Protocol approved: July 16, 2020

Study Title: Transcranial random noise stimulation (t-RNS) After Hand Recovery in Chronic Stroke

Clinical Trials.gov ID: NCT05489146

STUDY PROTOCOL

This is a double-blind pilot randomized control study. Individuals with moderate-to-severe stroke were randomly allocated to two groups:

Screening procedures

After obtaining the informed consent, potential participants were screened in more detail using a medical chart review and standardized clinical assessments.

Participants were recruited through referrals from the UPMC Rehabilitation Institute, UPMC Centers for Rehab Services, and the University of Pittsburgh Stroke Rehabilitation Research Network.

The following procedures were administered to screen potential participants:

- 1) We reviewed potential participants' medical charts after obtaining informed consent to confirm they have a primary diagnosis of unilateral hemiparesis due to a single episode of stroke, are 18 years or older, and that their onset of stroke is at least 6 months prior to study screening, have no history of schizophrenia, other neurological or medical conditions that would confound results.
- 2) We conducted a brief screen of upper extremity range of motion using a goniometer to determine if individuals are able to actively flex and extend the more-affected shoulder and elbow at least 30°.
- 3) We asked participants to follow directions to determine whether they have the ability to follow 3-step commands.
- 4) We conducted a brief cognitive screen using Mini Mental Status Examination to screen for cognitive impairments which may confound the results of the study.
- 5) We also conducted a brief mood screen using Patient Health Questionnaire-9 to screen for more than mild depression and question 16 and items of the (hypo) maniac module of the Mini-International Neuropsychiatric Interview Hybrid Assessment to screen for bipolar disorders.
- 6) We screened for one side neglect or hemispatial neglect using the Line Bisection Test, which is a quick paper-pencil test.
- 7) We also screened participants who do not show a motor evoked potential response of the wrist flexor and extensor muscle with the transcranial magnetic stimulation. This is important to determine whether there are some pathways from the damaged motor brain areas, which control the movement of the affected hand are intact. This will help to determine the responsiveness of the treatment, because it is futile to give to include and provide intervention to individuals who do not have any pathways (connectivity) intact between the damaged motor brain areas and the affected hand.

DETAILS OF THE SCREENING ASSESSMENTS (total participant time: 1 hour and 30

minutes):

1) Amount scale of Motor Activity Log (MAL):

The Amount scale of the Motor Activity Log measures the amount of use of the more-affected hand during activities of daily living. Items are scored on a 5-point ordinal scale with 0 representing the inability to use the more-affected upper extremity in daily living tasks in the last two weeks and 5 representing as much use of the more-affected hand in the last two weeks as compared to before the stroke. The MAL has been shown to have good reliability and validity.

Date: July 16, 2020

2). Visual Analog Scale (VAS):

The VAS quantifies the pain in the more-affected upper extremity using a 10-centimeter scale, with 0 representing no pain and 10 representing extreme pain. A cut-off score of 5 or greater will be used. The VAS has been shown to have good reliability and validity.

3). Modified Ashworth Scale (MAS):

The MAS is a clinical measure of muscle tone and involves the passive movement of the more affected shoulder, elbow, forearm, wrist, and fingers. The MAS has been shown to have good reliability and validity.

4) Mini-Mental State Examination (MMSE):

The MMSE is a clinical measure to examine the cognitive status and the ability to follow commands and ranges from 0-30. A cut-off score of more than 24 will be used. MMSE has good reliability and validity.

5) Patient Health Questionnaire (PHQ-9):

The PHQ-9 rates the severity of 9 symptoms of depression on a scale of 0 to 3. A cut-off score of more than 10 will be used. PHQ-9 has good reliability and validity.

6) Mini-International Neuropsychiatric Interview Hybrid Assessment (MINI):

Question 16 and items on the (hypo) maniac module will be used to screen bipolar disorders. An answer to "yes" to the questions and items will indicate bipolar disorders.

7) Line Bisection Test (LBT):

This scale is considered the gold standard in upper extremity rehabilitation trials and measures motor impairment by asking the participant to perform various arm and hand motions. Items are scored on a 3-point ordinal scale with 0 representing the inability to complete the item and 2 representing the ability to complete the item as asked. The FMUE has been shown to have good reliability and validity.

3) Stroke Impact Scale (SIS): to measure participation in daily life

The Stroke Impact Scale 3.0 (SIS) will be used to measure the impact of stroke on the participant's health and daily life. The SIS is a stroke-specific health outcome measure. It is a self-report measure and each item is scored on a 5-item Likert scale. We will complete items

from the hand subscale of SIS.

4) Action Research Arm Test (ARAT): to measure arm and hand recovery

The ARAT is a 19-item measure divided into 4 sub-tests (grasp, grip, pinch, and gross arm movement). The test takes 10 minutes to administer and has good reliability and validity.

Performance on each item is rated on a 4-point ordinal scale ranging from:

3: Performs test normally

2: Completes test, but takes abnormally long or has great difficulty

1: Performs test partially

0: Can perform no part of the test

4) Kinematic Measures of the upper extremity (UE) reaching (motion analysis procedures): to measure arm recovery

The data were collected using the Vicon Nexus three-dimensional motion analysis system. The Vicon is a passive infrared video-based motion analysis system. This system is capable of resolving motion in Cartesian space with an error of fewer than .5 millimeters. Calibration was completed both statistically and dynamically prior to each subject evaluation using standardized static and dynamic references. All data were collected and analyzed at 100 Hertz. Fourteen cameras were placed around the participant to obtain multiple views to construct 3D motion.

Participants were seated on a height-adjustable bench with feet flat on the floor. The weak UE was rested, palm down, on a low table placed alongside the weak lower extremity. The UE was in neutral shoulder flexion/extension and rotation and was adducted. Participants reached, pointed to a target, or grasped an object in front of them. Targets were placed at 80% of each participant's arm's length on a height-adjustable table. Participants reached each target five times first with their less-affected UE and then with their weak UE. In addition, participants also performed a table-wiping task for 1 minute. To minimize fatigue, a 1-minute rest break was provided between reaches.

Kinematics of reaches were also videotaped using a digital camera. Adhesive reflective markers (or spheres) were placed on various joints of the upper body including C7 and T10 vertebrae, the acromion process, clavicle, sternum, upper arm, lateral epicondyle of the elbow, forearm, wrist (VICON wrist band), dorsum of the hand, thumb fingertip, index fingertip, and the top of the target. These reflective markers were used to identify all targets and motion vectors of interest.

5) Electroencephalography (EEG) was used to record brain activity. EEG was recorded while the participant is attempting to perform movements of the weak UE, or while they are at rest. EEG uses sensors attached to the scalp (with tape or adhesive) to measure brain activity. We may use audio or visual cues to prompt the movements.

6) Basic Electromyography (EMG) was used to record muscle activity from a few muscles of the forearm. EMG sensors were attached to the forearm (with tape or adhesive) to measure muscle activity.

7) Transcranial magnetic stimulation (TMS) was used to record brain excitability. Participants

were seated comfortably in a chair with armrests in which they can keep their arms and hands in a constantly relaxed position. We placed 9mm Ag/AgCl surface electrodes over the flexor carpi radialis (FCR) and extensor carpi radialis (ECR) muscles. We delivered single pulse TMS using the Magstim system. The TMS coil was placed tangentially to the scalp with the handle pointing posteriorly. The stimulation was applied over the wrist/hand area of the affected motor cortex and individually localized for each participant based on the optimal position for eliciting MEPs. In order to keep the brain target constant throughout the stimulation session, we will use a frameless stereotactic neuronavigation system.

8) H-reflex (spastic reflex) testing was used to record the spastic reflex in the FCR muscle. H-reflex is the reflex reaction of the muscles after electrical stimulation of the peripheral nerves supplying the muscle. Elicitation of the FCR H-reflex itself is a common, harmless, minimally discomforting neurophysiological testing procedure performed in many laboratories and clinics worldwide. In order to elicit the FCR muscle H-reflex, we stimulated the median nerve on the volar surface of the forearm near the medial epicondyle using the surface Ag-AgCl electrodes and isolated constant current stimulation. We used the Digitimer DS7A system to stimulate the median nerve. The Digitimer DS7A system is an FDA-approved system to stimulate peripheral nerves. The response of the median nerve stimulation produces an H-reflex after 25-35 milliseconds, which were recorded by the EMG response from the 9mm Ag/AgCl surface electrodes placed over the FCR muscle. The EMG response from the FCR muscle were used to determine the H-reflex of the FCR muscle. In addition, to normalize EMG values of the FCR muscle, we recorded the M-wave from the EMG electrode of the FCR muscle, which is a response produced at 3-6 milliseconds after the median nerve stimulation. Similarly, in order to normalize the EMG value of the ECR muscle, we recorded the M-wave from the EMG electrode of the ECR muscle. In order to elicit an M-wave response for the ECR muscle, we stimulated the radial nerve on the dorsal surface of the forearm near the lateral epicondyle using the surface Ag-AgCl electrodes and the Digitimer DS7A.

Intervention procedures

Participants were randomized to one of the two intervention groups [transcranial random-noise stimulation (tRNS) and functional electrical stimulation (FES) or FES with sham tRNS] before pre-intervention testing. After randomization, participants underwent pre-intervention testing, followed by intervention 3 times per week for 6 weeks. Participants were enrolled for a total duration of approximately 5 months from pre-intervention to the follow-up phase. The intervention is described in the following paragraphs.

Experimental Group: Transcranial random-noise stimulation and functional training with FES.

The intervention was divided into two procedures:

1). Transcranial random-noise stimulation (tRNS):

The tRNS was applied with the StarStim device from Neuroelectrics Barcelona SL. The StartStim is battery-operated and has 8 channels that can provide low current brain stimulation. The maximum total current the device can output is 2mA (with a current precision of ~1micoA) using a maximum voltage of +/-15V. Participants received low-intensity current, which will not exceed 1.5mA for the first 30 minutes of the intervention while undergoing the 1st block (first 30

minutes) of functional training with FES. The Starstim was programmed such that the Starstim safely shuts off automatically after the first 30 minutes.

We used PiStim electrodes throughout the treatment, which have an area of 3.14 square cm. The Starstim system has a built-in function to adapt the current density to each type of electrode, such that no more than 1.5mA goes to every single electrode. This feature allowed us to safely administer the recommended current intensity throughout the treatment.

We applied electrodes (filled with the conductive gel) to the cleaned sites on the scalp and informed the participants that they might experience a slight tingling sensation during the inspection for scalp impedance. We began the Starstim stimulation protocol after determining that the scalp impedance for each electrode is less than 20 kOhm.

Before delivering the tRNS stimulation for 30 minutes, participants were provided a brief period of stimulation (less than 1 minute) and were asked if they can sustain this stimulation for the next 30 minutes. We immediately terminated the treatment if the participant was not willing to receive the treatment or if the participant reported any adverse events during the treatment.

The Starstim initially gradually ramped up the low-intensity current stimulation for the 1st minute, which is followed by continuous stimulation for the rest of the session.

2). Functional training with FES: Participants performed functional training with FES for one hour, three times a week for 6 weeks during each session of tRNS. Each one-hour session was divided into two-30 minutes blocks of functional training with FES. During the first 15 minutes of the 1st block, Neuromove, an FDA-approved device was used to facilitate wrist and finger flexion (wrist and finger flexor muscles) to practice grasping functional objects by closing the fingers with the Neuromove attached to their weak hand. During the next 15 minutes of the 1st block, the wrist and finger extension (wrist and finger extensor muscles) was facilitated using the same Neuromove device to practice releasing functional objects by opening the fingers with the Neuromove attached to their weak hand.

We repeated the 1st block, which now constituted the 2nd block. Similar to the 1st block, during the first 15 minutes of the 2nd block, we used Neuromove to facilitate wrist and finger flexion (wrist and finger flexor muscles) to practice grasping functional objects by closing the fingers with the Neuromove attached to their more-affected hand. During the next 15 minutes of the 2nd block, the wrist and finger extension (wrist and finger extensor muscles) was facilitated using the same Neuromove device to practice releasing functional objects by opening the fingers with the Neuromove attached to their weak hand.

A list of sample functional tasks is shown below. Participants chose 3 tasks and practice each task for 2 weeks.

Tasks

Reach and Grasp a can/cup, bring to mouth and then release on a surface

Picking and transferring small objects into container

Eating finger foods

Eating with spoon/fork

Picking thin books/note pads and placing them on a shelf

Placing coins

Picking the phone receiver, dialing with the less-affected hand, and placing the receiver.

Placing checkers in a game of connect 4

Opening pill boxes

We provided adequate rest breaks during the treatment if the patients feel tired during the treatment. Participants will only use the FES during research treatment. The Neuromove and the Starstim devices were not given to participants for their in-home use between the investigator's interventions. Participants also completed a tRNS and FES side effects questionnaire immediately after each treatment session.

Control Group: Functional training with FES with sham tRNS

The control group underwent similar functional training with FES but received sham tRNS.

Sham tRNS was delivered using the Starstim device. All the procedures of applying the electrodes and checking the impedance were the same for sham stimulation as well. During the stimulation, participants experienced a gradual ramp-up of the low-intensity current stimulation for the 1st minute, which gradually faded away after the 1st minute and participants did not receive any stimulation for the rest of the session.

We provided adequate rest breaks during the treatment if the patients felt tired during the treatment. Participants only used the FES during research treatment. The FES was not given to participants for their in-home use between the investigator's interventions.

All intervention sessions in both the experimental and control groups were videotaped. We randomly examine 15% of sessions in both groups and assess fidelity based on pre-defined principles.

Procedures to prevent interference between the devices:

In addition, all cables from the electrodes of the Starstim device are encased in a small unit that securely attaches to the participant's back of the head. This small unit then wirelessly communicated with the software on the computer. Thus, there were no hanging cables from the Starstim device.

Also, the electrodes of the Neuromove device are directly connected to the Neuromove device and are securely attached to the forearm muscles. Therefore, the two devices are never in direct contact, which will prevent any interference including leakage of current from the portable devices or leads during active treatment.

Procedures to monitor and recognize excessive cortical excitability:

During the treatment: The starstim has an in-built feature, which shuts automatically shuts off if the skin impedance is more than 2 kOhm.

Immediately after treatment: We will ask the participants to complete a tCS side effects questionnaire (attached) to document any side effects and provide adequate treatment if required.

POST-INTERVENTION ASSESSMENT

The assessments, which were administered pre-intervention were administered within one week after the completion of the intervention.

POST-2 (FOLLOW-UP) INTERVENTION ASSESSMENT

We administered the assessments again three months after the completion of the intervention.

STATISTICAL ANALYSIS

Linear mixed model analyses were used to test the added benefits of tRNS on upper-extremity function after stroke. This analysis was performed both for the primary (Fugl Meyer Upper Extremity Assessment) and secondary (grip strength, Wolf Motor Function Test, and hand subscale of stroke impact scale) outcome measures. The participant's group (tRNS, sham-tRNS), time (PRE, POST, POST-2), and group x time interaction were entered as the fixed independent variables along with baseline scores on the respective outcome measures as covariates in the model. Subject was included as a random effect in the model. A significant main or interaction effect was followed by post-hoc analyses using the Sidak multiple comparison procedure. An alpha level of $P<0.05$ was considered significant for all tests.

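### Passing the 20 kOhm start check does not assure a peak current near 1.5 mA: the ±15 V limit can cap it, or the 2 kOhm shut-off can interrupt it

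*Combined protocol and SAP*

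**What the plan says.** All the figures are in the protocol's Intervention procedures.

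- **Device limits** (Experimental Group, item 1, tRNS): "The maximum total current the device can output is 2mA (with a current precision of ~1micoA) using a maximum voltage of +/-15V". The device "has 8 channels that can provide low current brain stimulation", but the number of active and return electrodes is not stated.
- **Participant current** (same item): worded as a ceiling, "Participants received low-intensity current, which will not exceed 1.5mA for the first 30 minutes of the intervention". It is repeated per electrode: the system adapts the current "such that no more than 1.5mA goes to every single electrode". The text then adds: "This feature allowed us to safely administer the recommended current intensity throughout the treatment". No figure is attached to that intensity.
- **Start check** (same item): "We began the Starstim stimulation protocol after determining that the scalp impedance for each electrode is less than 20 kOhm".
- **Shut-off during treatment** (Procedures to monitor and recognize excessive cortical excitability): the device has a feature that "shuts automatically shuts off if the skin impedance is more than 2 kOhm".
- **Fidelity** (end of the Control Group text): all sessions are videotaped, and "We randomly examine 15% of sessions in both groups and assess fidelity based on pre-defined principles". No logging of delivered current or of voltage saturation is described.

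The Statistical Analysis section models group, time, their interaction and the baseline score. It has no term or summary for delivered current.

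**The concern.** The voltage limit, the current ceiling and the start impedance do not fit together if the intended peak is near the ceiling. An electrode can pass the start check and still have an impedance through which the stated voltage cannot drive that peak. The statement that the intended intensity was given throughout is then not assured by the procedure described.

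Active versus sham current is the only planned difference between the groups. If some active sessions were capped or interrupted, the dose in the active arm would depend partly on scalp contact and could vary between participants and sessions. A null result could reflect weak delivery rather than lack of effect, and a positive result would be tied to a dose that is not known. An analysis by group alone cannot separate these explanations.

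**Working it through.** The documents report no delivered current, so there is no figure of the plan's own to reproduce. The check is Ohm's law, V = I × R, with a resistive load and tissue resistance ignored.

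**Inputs from the protocol:** ±15 V; at most 1.5 mA; start check below 20 kOhm for each electrode; shut-off above 2 kOhm.

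**Assumptions, because the protocol is silent:** the intended peak is 1.5 mA; the montage; and whether ±15 V means 15 V or 30 V across the loop.

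**1. Voltage needed for 1.5 mA**
- One electrode at 20 kOhm: 1.5 × 20 = 30 V.
- Two such electrodes in series: 1.5 × 40 = 60 V.
- At 2 kOhm: 1.5 × 2 = 3 V for one electrode, 1.5 × 4 = 6 V for two.

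**2. Highest impedance for 1.5 mA, and peak current above it**

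| Reading | Highest impedance | At 15 kOhm | Limit at 20 kOhm |
|---|---|---|---|
| 15 V per electrode (same as 30 V across two in series) | 15/1.5 = 10 kOhm each | 15/15 = 1.0 mA | 15/20 = 0.75 mA (50%) |
| 15 V across a two-electrode loop | 15/1.5 = 10 kOhm loop, 5 kOhm each | 15/30 = 0.5 mA | 15/40 = 0.375 mA (25%) |
| 30 V, with 20 kOhm taken as the whole loop | 30/1.5 = 20 kOhm | 1.5 mA | 1.5 mA (100%) |

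The start check is strictly below 20 kOhm, so the last column gives bounds that are approached, not reached. On the first reading every accepted electrode gets more than half of 1.5 mA. On the second, half is reached at 10 kOhm each: 15/20 = 0.75 mA. The third reading removes the gap, but it departs from the protocol, which sets the limit for each electrode.

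**3. Several return electrodes.** With one active electrode and k equal returns, the loop is R(1 + 1/k). At R = 20 kOhm and k = 2, 4, 7:
- 15 V gives 0.50, 0.60 and 0.66 mA.
- 30 V gives 1.00, 1.20 and 1.31 mA.

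All are below 1.5 mA.

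**4. If 1.5 mA is peak-to-peak**, the peak is 0.75 mA.
- One electrode at 20 kOhm needs 0.75 × 20 = 15 V, which is just available.
- Two in series need 0.75 × 40 = 30 V, available if the loop has 30 V.
- If the loop has only 15 V, the limit is 15/0.75 = 20 kOhm, or 10 kOhm each, and the gap remains.

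**5. Peak is not RMS.** A voltage limit clips the peaks of a noise signal. For illustration, assume Gaussian noise with the 1.5 mA peak set at 2 or 3 SD. Clipped at c SD, its mean square (in SD²) is m(c) = 2Φ(c) − 1 − 2cφ(c) + 2c²(1 − Φ(c)). The share of RMS current kept is:
- Clipped at 0.75 mA: √(m(1)/m(2)) = √(0.516/0.921) = 75%, and √(m(1.5)/m(3)) = √(0.778/0.995) = 88%.
- Clipped at 0.375 mA: √(m(0.5)/m(2)) = √(0.185/0.921) = 45%, and √(m(0.75)/m(3)) = √(0.350/0.995) = 59%.

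The loss of RMS current is therefore smaller than the loss of peak current.

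**6. The shut-off.** At 2 kOhm the voltage needed (3 to 6 V) is well inside 15 V. If the shut-off works as written, stimulation stops long before the voltage limit binds. An electrode between 2 and 20 kOhm passes the start check and then triggers the shut-off.

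**The case against.** The strongest reply is that no stated dose is contradicted. The 1.5 mA figure is a ceiling, and a lower current breaks no sentence in the protocol. This stands as far as it goes: no target or minimum is given. But the protocol also says that a recommended intensity was administered throughout, and 1.5 mA is the only participant current it offers. For any intended peak above 0.75 mA per electrode (0.375 mA on the whole-loop reading), the start check does not support that statement.

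Second, the electrical conventions are open. A peak-to-peak reading can close the gap, and sharing 1.5 mA among several active electrodes would shrink it. This also stands, and it is why the point is conditional.

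Third, nothing shows that any electrode exceeded 5 or 10 kOhm; the protocol describes cleaned sites and gel-filled electrodes. That is correct. The point concerns what the procedure assures, not what happened.

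A reader might infer more: that active participants could receive half or less of a stated current with every rule kept, whatever the shut-off figure. The documents do not support this, for three reasons. Half or less requires 15 V to drive the whole series loop. The current is a ceiling, not a stated dose. And the 2 kOhm shut-off, taken as written, would stop stimulation before the voltage could limit it, so silent reduction needs that figure to be wrong or not in force, which the documents do not settle.

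**Conclusion.** The concern holds in conditional form. If the intended peak is near 1.5 mA, the stated voltage can deliver it only in the lower part of the impedance range that the start check accepts: half of that range on the per-electrode reading (10 of 20 kOhm), a quarter on the two-electrode whole-loop reading (5 of 20 kOhm). Near the top of the range, peak current could fall to just over half of 1.5 mA, or towards a quarter.

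The conclusion rests on the per-electrode wording of the start check, a resistive load, and 1.5 mA being the intended peak. It weakens or disappears on some peak-to-peak or shared-current readings. If the shut-off operates as written, the consequence is interrupted stimulation instead of reduced current. On neither account does passing the start check assure the intended current.

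This is possible under-delivery of unknown frequency. It is worth settling because it bears on the trial's only experimental contrast and no check of delivered current is described.

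**What to change.** 1. Reconcile the voltage limit, intended current and start impedance in the tRNS item together with the shut-off figure in the excitability-monitoring text. They should be settled jointly, since correcting the shut-off alone would leave the tRNS item unresolved. The sponsor decides which figure changes; this review takes no view on which is right.
2. State the intended current, whether it is peak, peak-to-peak or RMS, whether it applies per electrode or in total, and the montage. Say whether ±15 V applies per electrode or across the loop.
3. Summarise delivered current and any interruption per session in the active arm, from device output where it exists. Otherwise bound the current from recorded impedance where available. Where neither exists, say so.
4. Report the active dose as delivered.

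The cost is protocol wording and one per-session summary, which can still be produced after data collection if the records were kept. If the start check changes, some sessions may need a few more minutes of electrode preparation. The reported dose may look less favourable.

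### Side effects are asked about only at the end of each session: no described enquiry covers the interval before current is next applied or the period after session 18, and the listed in-session excitability measure is an impedance shut-off

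*Combined protocol and SAP*

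**What the plan says.** In the Experimental Group part of Intervention procedures, after the description of functional training: "Participants also completed a tRNS and FES side effects questionnaire immediately after each treatment session". The Control Group text does not repeat this sentence.

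A later section is headed "Procedures to monitor and recognize excessive cortical excitability". It lists two measures. During treatment, the device "shuts automatically shuts off if the skin impedance is more than 2 kOhm". The other entry reads "Immediately after treatment: We will ask the participants to complete a tCS side effects questionnaire (attached) to document any side effects", and adds that treatment is provided if needed. This section names no arm, and the attached form is not part of the public text.

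The tRNS subsection has two further safeguards. After a trial of current lasting under a minute, participants "were asked if they can sustain this stimulation for the next 30 minutes". Treatment is ended if the participant is unwilling or reports an adverse event while it is under way. The same subsection gives an electrode condition for starting: "We began the Starstim stimulation protocol after determining that the scalp impedance for each electrode is less than 20 kOhm".

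Item 7 of the pre-intervention assessment says how excitability is measured: "Transcranial magnetic stimulation (TMS) was used to record brain excitability". On the visit after the course, the protocol says: "The assessments, which were administered pre-intervention were administered within one week after the completion of the intervention". The three-month visit administers the assessments again. None of the listed pre-intervention assessments is a side-effect query.

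**The concern.** The protocol itself names excessive cortical excitability as something to be monitored and recognised, and it exposes each participant to a course of repeated sessions. A symptom that begins after the participant has gone home falls outside every scheduled question, unless the end-of-session form happens to look back. Even then, the form is completed after the next stimulation. After the last session no form follows at all.

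Two things are at stake. The team has no planned enquiry about the preceding days before re-exposure. And any statement about tolerability will rest on a collection period that the documents do not define. Without a rating on arrival, it may also be hard to separate symptoms the participant brought to the session from symptoms that arose in it.

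The in-session entry under the excitability heading adds to the problem. A reader would take it as surveillance of the brain's response, but it is a property of the electrode contact.

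**Working it through.** The documents give no adverse-event rate, onset time or sample size, so there is no planned figure to reproduce. The check is a count on the schedule and a reading of each point of contact.

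Inputs: sessions 3 times a week for 6 weeks (Intervention procedures); one-hour sessions (Functional training with FES); visits within one week and at three months after the course (the two post-intervention sections).

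- Sessions: 3 × 6 = 18.
- Intervals between sessions: 18 − 1 = 17, plus one open period after session 18.
- Average spacing, assuming even spread over the week: 7 × 24 / 3 = 56 h from start to start, so 56 − 1 = 55 h outside the session.

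| Point of contact | What is described | Asks about the time since the last session? |
|---|---|---|
| Before stimulation | Electrode impedance check | No |
| Before the 30-minute stimulation | Short trial of current, then a tolerance question | No; it looks forward, and current has already been applied |
| During stimulation | Treatment ended on unwillingness or a reported adverse event | No; that session only |
| End of session | Questionnaire | Unknown; form not shown |
| POST | Pre-intervention assessments repeated | No side-effect item listed |
| POST-2 | Same assessments again | No side-effect item listed |

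The recall window is the one unknown that matters, so take both ends of the range.

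- If the form covers only the session just finished, scheduled questioning covers 0 of the 18 post-session periods.
- If the form looks back to the previous visit, it covers 17 of 18. Each of those 17 is asked about only after the next stimulation has been given. The 18th has no later form.

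In both cases, 0 of the 17 intervals are the subject of a described question before current is next applied, and the period after session 18 is not asked about.

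On the excitability heading: the protocol's measure of excitability is TMS, which appears at screening (motor evoked potential response) and at PRE, POST and POST-2. None of these falls within the 18-session course. Impedance is used in the tRNS subsection as a per-electrode condition for starting. The two impedance figures also conflict. Starting requires less than 20 kOhm and shut-off occurs above 2 kOhm, a ratio of 20 / 2 = 10. Taking scalp and skin impedance to be the same quantity, any electrode between 2 and 20 kOhm meets the start condition and also exceeds the shut-off limit.

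**The case against.** The strongest reply is that the questionnaire cannot be seen. When a form is completed is not the same as the period it covers; it may look back, and it may ask about symptoms already present on arrival. Spontaneous reports are not excluded. The participant has a checkpoint before each 30-minute stimulation and can decline there. Adverse events reported in session end the treatment, and the questionnaire is tied to providing treatment. TMS at POST and POST-2 gives a measure of excitability after the course. The Statistical Analysis section plans no safety endpoint, and if both arms use the same form, pre-existing symptoms should be similar on average between randomised groups.

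Much of this stands, and it rules out several stronger conclusions that a reader might draw:

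- That delayed events are lost. The unseen recall window and the possibility of spontaneous reports do not allow this; they are only not systematically asked about.
- That the form covers 1.8% of the course. The arithmetic is right (18 × 1 h = 18 h; 6 × 168 h = 1,008 h; 18 / 1,008 = 1.8%), but it divides session time by calendar time. It measures neither the period the form covers nor the share of events recorded.
- That nothing is collected after session 18. A form closes that session and two assessment visits follow; what is absent is a described side-effect query at those visits.
- That the team has no trigger to act, or that symptoms present on arrival are necessarily counted as side effects. The tolerance question, the termination rule and the unseen form contradict the one and leave the other open.

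The reply does not close the gap. The tolerance question concerns the coming 30 minutes and follows a trial of current. The termination rule covers the session under way. TMS at an assessment visit is not a question about symptoms.

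**Conclusion.** The point holds as a gap in systematic enquiry. For all 17 between-session intervals, no question about the interval is described before current is next applied. For the period from the end of session 18 to three months, no side-effect query is described. Neither statement depends on the form's recall window. No share of events missed can be computed, and none should be quoted.

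The point also holds on labelling: by the protocol's own use, the impedance shut-off is an electrode check and does not measure cortical excitability.

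Assumptions: the side-effects form named in the Experimental Group text and the one named under the excitability heading are the same or are given at the same time; the trial of current and the tolerance question occur at each session; sessions are evenly spaced (this affects only the 55 h figure).

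The primary and secondary efficacy analyses are unaffected. The gap limits what can be said about safety, and it should be corrected because correction is cheap.

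**What to change.** In both arms, keep the end-of-session questionnaire and add the same form at three further points: at the start of every session before any current is applied, covering the time since the last session; at POST, covering the time since session 18; and at POST-2. State the form's recall window, say explicitly that it applies to the control group, and define the adverse-event collection period up to three months. How staff act on the answers is for the investigators to decide.

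Describe the impedance shut-off as an electrode-contact safeguard and not as a monitor of excitability. Reconcile the start condition (below 20 kOhm) in the tRNS subsection with the shut-off (above 2 kOhm) in the excitability section.

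The cost is a short amendment and a few minutes per visit, using an existing form at visits already scheduled. The small downside is that more minor events will be recorded.

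Much of the protocol is in the past tense. If treatment is already complete, the action is to state wherever safety is reported that scheduled questioning took place only at the end of each session, with the form's recall window, and that the documents describe no side-effect query after session 18.
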